6.2.2 Secondary Efficacy Analysis

6.2.2.1 Secondary efficacy endpoints

The secondary efficacy variables are specified below.

- Overall survival
- Time to first SSE
- Radiological progression-free Survival (rPFS)
- Time to radiological progression (TTP)
- Pain improvement rate
- Time to pain progression

Overall survival is defined for each comparison as the time (days) from the applicable start date to the date of death due to any cause. See [Table 9–3](#) in Appendix 9.1.2 for detailed censoring rules.

Comparison 1:

Arm C subjects who have died or are known to be alive after ‘pooling cut-off date’ will be censored on the ‘pooling cut-off’ date. Refer to Section 4.5 for pooling cut-off date.

All other subjects in arms A, B and C, refer to [Table 9–3](#) for censoring rules.

Overall Survival (OS) following randomization = End Date – Date of Randomization +1

Comparison 2:

For Comparison 2 eligible subjects, refer to [Table 9–3](#) for censoring rules.

Overall Survival (OS) following Week 24 baseline = End Date – Date of Week 24 baseline(the 6th dose date) +1

Time to first symptomatic skeletal event is defined for each comparison as the time (days) from the applicable start date to the date of the first SSE. See

[Table 9–4](#) in Appendix 9.1.3 for detailed censoring.

Time to radiological progression is defined for each comparison as the time (days) from the randomization date to the date of the first radiological progression. Comparison 2 will not follow the Week-24 baseline and randomization baseline will be used instead. See [Table 9–5](#) and [Table 9–6](#) in Appendix 9.1.4 for detailed censoring rules.

The central reviewer will evaluate the radiological imaging produced by the investigator. Primary radiological progression endpoints will be based on the central radiological reviewer assessments. Investigator assessments will be provided as a sensitivity analysis.

Radiological progression of soft-tissue disease is determined according to modified RECIST criteria, version 1.1 (See Protocol Section 14.1) based on MRI / CT scans of the chest, abdomen, and pelvis.

Radiological progression of bone disease is determined according to adapted PCWG2 criteria (see Protocol Section 14.2) based on whole body technetium-99 bone scans.

Radiological progression of bone disease requires confirmation. A subject is considered to have progressed by bone scan if:

- The first bone scan with ≥ 2 new lesions compared to baseline is observed < 12 weeks from randomization and is confirmed by a second bone scan taken ≥ 6 weeks later showing ≥ 2 additional new lesions (a total of ≥ 4 new lesions compared to baseline); or
- The first bone scan with ≥ 2 new lesions compared to baseline is observed ≥ 12 weeks from randomization and the new lesions are verified on the next bone scan ≥ 6 weeks later (a total of ≥ 2 new lesions compared to baseline).

The date of progression of bone disease will be the date of the first observed bone progression, not the date that confirmed the bone progression.

The date of radiological progression will be determined following the rules in [Table 9–6](#).

Radiological progression-free survival is defined for each comparison as the time (days) from the randomization baseline to the date of radiological disease progression or death from any cause (if death occurs without prior progression). See [Table 9–7](#) in Appendix 9.1.5 for detailed censoring rules for both Comparison 1 and Comparison 2.

If data permits, unconfirmed radiological progression-free survival and time to unconfirmed radiological progression will be analyzed as sensitivity analyses based on central reviewer. Bone progression in this case does not require confirmation.

Pain endpoints

The pain data collected from ePRO will be used for these analyses.

Worst pain score (WPS) at a given visit is defined for each subject as the mean of the 7 day “worst pain score” assessments taken on or before each applicable visit. If less than 4 non-

missing WPS values are available for a given visit, then the weekly worst pain score will be left missing for that visit.

Timepoint pain improvement rate is defined with respect to each applicable baseline as the proportion of subjects with a 30% and 2-point decrease in WPS with respect to the applicable baseline assessment over 2 consecutive assessment periods conducted at least 3 weeks apart among subjects with a WPS score ≥ 4 at the applicable baseline. The first of the 2 consecutive periods is taken to be the date of improvement.

Time to pain progression is defined for each comparison in subjects with a WPS of ≤ 7 at the applicable baseline as the time from the applicable start date to an increase of 2 or more points in WPS (with respect to the applicable baseline). Refer to

Table 9–4 in Appendix 9.1.3 for detailed censoring rules.

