6.2.1 Primary Efficacy Analysis

The primary efficacy endpoint, symptomatic skeletal event-free survival (SSE-FS), will be defined separately for each of the two efficacy evaluations described above, as follows:

For Comparison 1, SSE-FS following randomization is defined in ITT subjects as the time from randomization to an SSE or death, whichever occurs first. Refer to Appendix 9.1.1 for censoring rules.

For Comparison 2, SSE-FS from 6th dose is defined in W24 subjects as the time from Week 24 baseline (the 6th dose date) to an SSE or death, whichever occurs first. Refer to Appendix 9.1.1 for censoring rules.

For both evaluations, a symptomatic skeletal event (SSE) is defined as follows:

- The use of external beam radiotherapy (EBRT) to relieve skeletal symptoms
- The occurrence of new symptomatic pathological bone fractures (vertebral or non-vertebral)
- The occurrence of spinal cord compression
- A tumor related orthopedic surgical intervention.

The censoring rules for SSE-FS for each comparison are summarized in [Table 9–1](#) and [Table 9–2](#) of [Appendix 9.1.1](#). Stratified statistical tests described in this section refers to two of the three randomization strata as determined by the IXRS: use of prior chemotherapy (≤ 1 regimen versus > 1 regimen), and total ALP (< 220 U/L versus ≥ 220 U/L). Note that Average worst pain score (WPS) was included as one of stratification factor for randomization in order to balance the baseline pain across three arms. However, WPS will not be included in the analysis to avoid sparse cells due to relatively small sample size within each arm.

Each analysis will use a stratified log-rank test. A one-sided significance level of 0.10 will be used for interpretation of the results. Additionally, the hazard ratio (respectively high dose/standard dose and extended dose/standard dose) will be computed together with the two sided -80% and -95% CIs using a stratified Cox regression model. There will be no adjustment for multiple comparisons.

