6.2.2.2 Analysis of secondary efficacy endpoints

The following secondary efficacy time-to-event endpoints will have hypothesis testing performed for both Comparison 1 and Comparison 2: OS, time to first SSE, time to radiological progression, and rPFS.

A one-sided type I error rate of 0.10 will be used for secondary efficacy endpoint hypothesis testing.

Hypothesis tests for these endpoints will be performed using a stratified log-rank test accounting for the same two randomization stratification factors as for the primary endpoint analysis (See Section 6.2.1). The treatment effect (hazard ratio) will be estimated using the Cox proportional hazards regression model stratified by the above-mentioned two randomization stratification factors. For rPFS and time to radiological progression, analyses will be done based on both the investigator's and the independent assessments. Analysis based on the independent central review assessment will be considered the primary analysis for rPFS.

Secondary efficacy time-to-event endpoints will be summarized using Kaplan-Meier [5] estimates. Median survival time together with the 25th and 75th percentiles and associated 80% and 95% Brookmeyer-Crowley [6] confidence intervals (CI) will be presented by group. Corresponding Kaplan-Meier [5] curves will be generated by group.

Pain improvement rate will be calculated for each post-baseline timepoint, with exact binomial 80% and 95% Clopper-Pearson [7] confidence intervals. Pain improvement rate with exact binomial 80% and 95% CIs will also be plotted by timepoint.

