Each standardized analgesic name will be classified by strength type as non-opioid, weak opioid, or strong opioid.

An increase in analgesic use following randomization baseline is defined in Table 6–3 below. If a subject is using more than one type of analgesic, the strongest type will be used in the analysis.

Table 6–3 Increase in Analgesic Use Algorithm

Baseline intake	Post baseline
No analgesics or a non-opioid	Initiation of any opioid
Weak opioid	Initiation of any strong opioid or adding an additional weak opioid
Strong opioid	Initiation of an additional strong opioid

Pain improvement rate without increase in analgesic use following baseline is defined at each post-baseline assessment time point as the proportion of subjects with a 30% and 2-point decrease in average WPS over 2 consecutive assessment periods conducted at least 4 weeks apart, without a corresponding increase in analgesic use over those 2 periods. The denominator is the number of subjects with a non-missing WPS of at least 4 at randomization.

Time to increase in analgesic use is defined as the time in days from randomization baseline until the first increase in analgesic use for subjects with baseline average WPS of ≤ 7 and non-missing baseline assessment of analgesic use. See Table 9–5 in Appendix 9.1.4 for detailed censoring rules.

Pain progression or increase in analgesic use following baseline is defined as the time in days from randomization baseline until the earlier of pain progression or a first increase in analgesic use for subjects with a non-missing baseline average WPS of ≤ 7 . See [Table 9–4](#) in [Appendix 9.1.3](#) for detailed censoring rules.

Change in analgesic use following baseline : A shift table will be presented to summarize the change in strength of analgesic use from randomization baseline to the strongest use at post-baseline. The strength type will include: no analgesics or non-opioid, weak opioid, and strong opioid.

NCCN-FACT FPSI-17 Endpoints

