Each subject will fill out the complete 11-question BPI-SF using an ePRO device at the Treatment Day 1 visit and at each clinic visit thereafter through Week 48. For subjects in Arm A and Arm B, the modified complete BPI-SF will also be filled out on the day of telephone contacts scheduled for Weeks 28, 32, 40, and 44. The data will be collected for one week (6 days prior to the applicable visit and the morning of the visit) prior to each clinic visit or phone call follow-up.

The BPI-SF (Protocol Section 14.9) is a short, self-administered questionnaire with 11 items, which was designed to evaluate the intensity of, and the impairment caused by pain. All BPI-SF items are scored using rating scales. Four items measure pain intensity (pain now, average pain, worst pain, and least pain) using 0 (“no pain”) to 10 (“pain as bad as you can imagine”) numeric rating scales, and seven items measure the level of interference with function caused by pain (general activity, mood, walking ability, normal work, relations with other people, sleep and enjoyment of life) using 0 (no interference) to 10 (complete interference) rating scales.

The items are aggregated into two dimensions, (1) **Pain severity index**, using the sum of the four items on the pain intensity, and (2) **Function interference index**, using the sum of the seven pain interference items (at least 4 out of 7).

Each BPI-SF subscale, and the two indices for pain severity and function interference, will be summarized using descriptive statistics.

Weekly Average pain score (APS) is defined for each subject at baseline and at each post-baseline date, as the mean of the “average pain score” values in the last 24 hours from the preceding 7 days before each applicable visit or telephone contact per the BPI-SF.

Analysis of Exploratory Endpoints

Identical statistical methods for analyzing time-to-event secondary endpoints, as elucidated in section 6.2.2.2, will be applied to the analysis of time-to-event exploratory endpoints:

- Time to radiological bone progression
- Time to radiological soft-tissue progression
- Time to total alkaline phosphatase (ALP) progression
- Time to ALP progression without 12-week restriction
- Time to PSA progression
- Time to PSA progression without 12-week restriction
- Time to pain progression or increase in analgesic use following baseline
- Time to increase in analgesic use
- Time to increase in physical symptoms of disease based on FPSI-DRS-P

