6.2 Efficacy

Refer to the main SAP v2.0 dated 17 MAY 2017.

Pain improvement rate at week 12, week 24, EOT, and overall will be summarized by including all subjects in ITT population as denominator. Same analyses will be repeated for week 24 analysis set.

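### Both pain improvement rates count falls in worst pain recorded after palliative radiotherapy or orthopaedic surgery, so a regimen with more of these interventions can gain improvers

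*SAP*

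**What the plan says.** **Secondary rate.** SAP section 6.2.2.1 defines the timepoint pain improvement rate as "the proportion of subjects with a 30% and 2-point decrease in WPS with respect to the applicable baseline assessment". The fall must hold "over 2 consecutive assessment periods conducted at least 3 weeks apart among subjects with a WPS score ≥ 4 at the applicable baseline". The definition says nothing about other pain-relieving treatment.

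**Analysis.** Section 6.2.2.2 states: "Pain improvement rate will be calculated for each post-baseline timepoint, with exact binomial 80% and 95% Clopper-Pearson [7] confidence intervals". The rate is not among the secondary endpoints listed there for hypothesis testing, which are OS, time to first SSE, time to radiological progression and rPFS.

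**Co-primary endpoint.** Section 6.2.1 lists as an SSE "The use of external beam radiotherapy (EBRT) to relieve skeletal symptoms". Tumour-related orthopaedic surgery is on the same list.

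**Exploratory variant.** Section 6.2.3.1.1 adds a rate that requires improvement "without a corresponding increase in analgesic use over those 2 periods". It does not mention radiotherapy or surgery.

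**Data collection.** Section 6.2.3.1.1 also states: "Each subject will fill out the complete 11-question BPI-SF using an ePRO device at the Treatment Day 1 visit and at each clinic visit". Collection runs through Week 48, and no stop after an SSE is stated.

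**Supplements.** Section 6.2 of both Supplemental SAPs (v1.0 and v2.0) adds: "Pain improvement rate at week 12, week 24, EOT, and overall will be summarized by including all subjects in ITT population as denominator". The same is repeated for the Week 24 set. Only the denominator changes.

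**The concern.** EBRT given to relieve skeletal symptoms is intended to lower pain. A man who receives it has failed SSE-FS. If his WPS then falls far enough below baseline in two periods, he is scored as a pain improver for his assigned regimen. The same applies after orthopaedic surgery. The regimen with more of these interventions has more chances to collect such improvers, so the pain rate can drift towards the arm that does worse on the co-primary endpoint and hide a real difference in pain between regimens.

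The SAP already accepts this reasoning for drugs, since the exploratory variant excludes relief that coincides with stronger analgesia. It leaves out the two non-drug interventions that it classes as skeletal events.

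**Working it through.** **1. Is there a rule anywhere?**

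| Place in the SAP | Rule on WPS after EBRT or orthopaedic surgery |
|---|---|
| 6.2.2.1, secondary pain rate | None |
| 6.2.2.2, analysis of the rate | None |
| 6.2.3.1.1, rate without increased analgesic use | Analgesics only |
| 6.2.3.1.1, BPI-SF collection | No stop after an SSE |
| Table 9–4 | Time-to-event endpoints only; no EBRT row |
| Tables 9–5 and 9–7 | New systemic anti-cancer treatment, imaging endpoints only |
| Supplemental SAPs v1.0 and v2.0, 6.2 | Denominator only |

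For Comparison 2, the Week 24 set is defined by number of injections, so it can include men with an SSE before the 6th dose. Table 9–2 and section 9.1.3 deal with them for the time-to-event endpoints. Nothing does so for the pain rate.

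**2. Inputs for a size.** The SAP states no expected pain rate, so there is no figure to reproduce. The illustration uses:
- Median SSE-FS of 9 months (standard dose) and 13.5 months (high dose), from section 3.4. Arms A and B are compared directly, because section 6.2 does not pool Arm C for non-time-to-event endpoints.
- Assumed, not in the SAP: share *s* of SSE-FS events that are EBRT, 30% to 70%.
- Assumed, not in the SAP: share *r* of irradiated men who then meet the pain criterion, 30% to 70%.

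**3. Check of the exponential model.** 24 weeks = 168 / 30.4375 = 5.52 months. With a 9-month median and 3% monthly loss, event or loss by 24 weeks is 1 − exp(−(ln 2 / 9 + 0.03) × 5.52) = 44.6%. Reading the loss as −ln(0.97) gives 44.7%. The SAP states 44.65%, so the model matches the SAP's own.

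**4. SSE-FS event by Week 24.** F = 1 − exp(−ln 2 × 5.52 / median):
- 9 months: F = 0.346
- 13.5 months: F = 0.247

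**5. Points added to the rate by Week 24** = 100 × F × *s* × *r*:

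| *s*, *r* | 9 months | 13.5 months | Difference |
|---|---|---|---|
| 30%, 30% | 3.1 | 2.2 | 0.9 |
| 50%, 50% | 8.7 | 6.2 | 2.5 |
| 70%, 70% | 17.0 | 12.1 | 4.9 |

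At 50% and 50%, the arm with more events gains up to about 2.5 points more, without any true difference in pain control.

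**6. Scale against sampling error.** Suppose all 360 / 3 = 120 men per arm had a baseline WPS of at least 4. The 80% half-width for a difference between two rates is 1.2816 × √(2p(1 − p)/120). That is 7.6 points at p = 0.3 and 8.3 points at p = 0.5. The illustrated bias is smaller than this, but it is systematic.

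**The case against.** **A legitimate choice of estimand.** Counting WPS regardless of later treatment is a recognised treatment-policy approach, and the definition is otherwise complete. Time to pain progression has no EBRT rule either. This stands to the extent that the SAP does not contradict itself. However, the choice is never stated as one, and the guarded variant shows that other pain treatment was meant to be examined.

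**Nothing is tested.** This stands. A reader might infer that a type I error rate or a formal conclusion is at risk. Section 6.2.2.2 gives this rate only confidence intervals and plots.

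**Every arm receives radium-223.** This stands. A reader might infer that radiotherapy relief would be claimed as a success of radium-223 itself. There is no arm without radium-223, so only a difference between regimens in these interventions matters.

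**EBRT is reported alongside.** Section 6.2.1 asks for the contribution of each SSE component, and section 6.1.5 summarises radiotherapy for the ITT and Week 24 populations. A reader can see an imbalance in EBRT but cannot correct the pain rate for it.

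**The size is assumed and generous.** This stands. Some irradiated men would have improved anyway. The fall is measured from baseline, not from the pain level before EBRT. The main SAP's rate is per timepoint, so EBRT after a timepoint's assessments cannot raise it. The cumulative sum fits the supplements' overall rate better.

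**Failing men for any SSE would overreach.** This also stands. A reader might infer that improvement should have to precede every kind of SSE. Fracture or cord compression alone is not a pain treatment. In Comparison 2, events before the 6th dose precede the divergence of the regimens.

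**Conclusion.** The point holds as a modest weakness in how a descriptive secondary endpoint is defined. Both pain improvement rates count relief recorded after EBRT for skeletal symptoms or tumour-related orthopaedic surgery. The bias favours the regimen with more of these interventions. Under the SAP's own alternative for Comparison 1, that would be the standard dose, so a real pain advantage of the high dose would be understated.

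The size cannot be fixed from the SAP. The 2.5 points by Week 24 rest on the 9 and 13.5 month medians, a 50% EBRT share and a 50% response. They are a ceiling for those shares, because they assume that no irradiated man would otherwise have improved and that two later assessments are always available. They also assume that men with a baseline WPS of at least 4 have the overall SSE-FS. Surgery, and EBRT after another first SSE, are left out of the sum.

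**What to change.** 1. **Exploratory rate (6.2.3.1.1).** Extend the guard so that a man counts as improved only if he also had no EBRT for skeletal symptoms and no tumour-related orthopaedic intervention between the applicable baseline and the end of the second qualifying period.
2. **Secondary rate (6.2.2.1, and section 6.2 of both supplements).** Report it in two ways: regardless of these interventions, as now; and with assessments after them scored as not improved, keeping those men in the denominator.
3. **Limits.** Do not count fracture or spinal cord compression alone as a failure. For Comparison 2, do not count interventions before the Week 24 baseline.

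The change needs SAP wording and a date check against SSE data already collected. It adds one rate to the tables, and the guarded rates will be somewhat lower.

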6.2.2.2 Analysis of secondary efficacy endpoints

The following secondary efficacy time-to-event endpoints will have hypothesis testing performed for both Comparison 1 and Comparison 2: OS, time to first SSE, time to radiological progression, and rPFS.

A one-sided type I error rate of 0.10 will be used for secondary efficacy endpoint hypothesis testing.

Hypothesis tests for these endpoints will be performed using a stratified log-rank test accounting for the same two randomization stratification factors as for the primary endpoint analysis (See Section 6.2.1). The treatment effect (hazard ratio) will be estimated using the Cox proportional hazards regression model stratified by the above-mentioned two randomization stratification factors. For rPFS and time to radiological progression, analyses will be done based on both the investigator's and the independent assessments. Analysis based on the independent central review assessment will be considered the primary analysis for rPFS.

Secondary efficacy time-to-event endpoints will be summarized using Kaplan-Meier [5] estimates. Median survival time together with the 25th and 75th percentiles and associated 80% and 95% Brookmeyer-Crowley [6] confidence intervals (CI) will be presented by group. Corresponding Kaplan-Meier [5] curves will be generated by group.

Pain improvement rate will be calculated for each post-baseline timepoint, with exact binomial 80% and 95% Clopper-Pearson [7] confidence intervals. Pain improvement rate with exact binomial 80% and 95% CIs will also be plotted by timepoint.

6.2.3 Exploratory Analysis

For exploratory radiological endpoints, only central reviewer assessments will be analyzed.

6.2.3.1 Exploratory endpoints

The exploratory variables are specified below:

- Time to radiological bone progression
- Time to radiological soft-tissue progression
- Patient bone scan lesion area (BSLA)
- Patient bone scan time point response rate (week 8, week 16 and week 24) and best overall response rate, based on central review
- Total alkaline phosphatase (ALP) response rate
- Time to total alkaline phosphatase (ALP) progression
- Time to total alkaline phosphatase (ALP) progression without 12 week restriction
- Percentage change in total alkaline phosphatase (ALP) at 12 and 24 weeks
- Prostate specific antigen (PSA) response rate
- Time to PSA progression
- Time to PSA progression without 12 week restriction
- Pain improvement rate without increase in analgesic use (week 12, week 24, EOT and overall)
- Time to pain progression or increase in analgesic use
- Change in analgesic use
- Time to increase in analgesic use
- NCCN-FACT FPSI-17 subscale scores
 - FPSI Disease Related Symptoms – Physical (DRS-P)
 - FPSI Disease Related Symptoms – Emotional (DRS-E)
 - FPSI Treatment Side Effects (TSE)
 - FPSI Function/Well Being (F/WB)
- Time to increase in physical symptoms of disease based on FPSI-DRS-P
- BPI-SF subscale scores and aggregate indices
 - BPI-SF Pain Severity Index
 - BPI-SF Function Interference Index
- Average Pain Score (APS)

